5.3 Identity of Investigational Product

SKI-O-703 capsule is a Swedish orange capsule and will contain the active ingredient SKI-O-703 (100 mg). Placebo capsules will be identical in appearance and weight to the SKI-O-703 capsule and contain microcrystalline cellulose and magnesium stearate.

Oscotec Inc. will provide adequate supplies of blinded SKI-O-703 and placebo capsules to the study site.

5.4 Management of Clinical Supplies

5.4.1 Study Drug Packaging and Storage

SKI-O-703 (100 mg) capsules and matching placebo capsules will be manufactured using ProFill® capsule filler, packaged 70 count each into high density polyethylene bottles, and shipped to the study site. Study drug will be packaged and labeled according to applicable local and regulatory requirements.

Study drug must be stored in accordance with the manufacturer's instructions. The storage conditions and expiry or retest date will be indicated on the label. At the study site, study drug must be stored in a limited access, securely locked area and kept at a controlled room temperature between 15°C and 30°C.

5.4.2 Test Article Accountability

The investigator or pharmacy designee will maintain accurate records of receipt of all test articles, including dates of receipt from sponsor, assignment and dispensation to the subject(s), return from subject(s), and destruction of returned IMP (and/or return to the depot for destruction). This is denoted as pharmacy IMP accountability.

In addition, accurate records will be kept by the responsible site personnel regarding when and how much test article is dispensed to, used by, and returned from each subject in the study. At each study visit requiring dispensation (Visit 1, 3, and 4), a new set of 4 bottles of IMP will be dispensed to the subject to cover that study visit period and the previous set of 4 bottles will be collected. Subject dosing will be recorded on a subject dosing diary. Subjects will be instructed to return all drug containers (even if empty) to the study site personnel at each clinic visit. Site personnel will document compliance and reasons for departure from the expected dispensing regimen in study source documents. This is denoted as subject IMP accountability.

At the completion of the study, to satisfy regulatory requirements regarding drug accountability, all study drugs will be reconciled and retained or destroyed according to applicable regulations.

5.5 Overdose Management

An overdose is any dose of study drug given to a subject or taken by a subject that exceeds the dose described in the protocol. Overdoses without signs or symptoms do not need to be recorded as AEs; in case of any AEs associated with the overdose, these should be reported on relevant AE/SAE sections in the eCRF.

Overdoses (including those without signs or symptoms) and medication errors should be documented in the PIP system as protocol deviations and communicated to the clinical study manager and/or safety manager.

No specific therapy for an overdose of SKI-O-703 exists. In the event of an overdose or medication error, therapy appropriate for the subject's symptoms and clinical status should be provided.

5.6 Blinding

This is a double-blind study. Neither the subjects nor the investigator/site personnel will be aware of the treatment assignment for the subjects in each cohort. Additionally, the study drugs will be identical in number and appearance for each cohort. Blinding will be maintained throughout the study by use of active or placebo dosage forms of similar appearance.

5.6.1 Breaking the Blind

A subject's treatment assignment will not be broken until the end of the study unless medical treatment of the subject depends on knowing the study treatment the subject received. In the event that the blind needs to be broken because of a medical emergency, the investigator can unblind an individual subject's treatment allocation. The treatment assignment will be unblinded through IxRS.

As soon as possible, the investigator should first contact the medical monitor to discuss the medical emergency and the rationale for revealing the actual treatment received by that subject. Reasons for treatment unblinding must be clearly explained and justified in the eCRF. The date on which the code was broken together with the identity of the person responsible must also be documented.

5.7 Treatment Compliance

All doses must be taken in accordance with the original dosing schedule outlined at subject's Day 1 visit with the first dose. All doses must be taken approximately 12 hours (± 2 hours) after the previous dose in a consistent BID dosing pattern.

All IMP consumed must be documented clearly on the subject's dosing diary for accountability purposes. Each subject's dosing diary should be closely monitored by the site personnel at each study visit to ensure compliance with the original dosing schedule, beginning with the first dose of study drug has been maintained.

Missed Dose(s)

If the subject does not take their study drug dose at their regularly scheduled dosing time, they should take the dose as soon as possible but at least 8 hours before the next scheduled dose. If the next scheduled dose is within an 8 hours window, the dose is considered missed, and the subject should resume dosing with the subsequent dose on the original schedule.

If the subject experiences any drug interruption(s) they should notify their study site physician during the next scheduled study visit. Missed doses should be reported as a protocol deviation (or violations depending on the number of doses missed) may result in data that are not deemed evaluable (by the investigator) for a protocol analysis and/or may require subject(s) to be discontinued.

5.8 Prior and Concomitant Therapy

Use of all concomitant medications that the subject is receiving at the time of screening or receives during the study must be recorded in the subject's eCRF. The minimum requirement is the drug name and the dates of administration (including start and end dates), dosage information including dose, route and frequency, and reason for drug use are to be recorded in the eCRF. This will include all prescription drugs, herbal products, vitamins, minerals, vaccines, over the counter medications (including folic acid or equivalent), and food products listed in Appendix 13.1 and in prohibited medications (Section 5.8.2). Any changes in concomitant medications also will be recorded in the subject's eCRF.

5.8.1 Permitted Concomitant Medications

Any concomitant medication, except the prohibited medications (Section 5.8.2), deemed necessary for the welfare of the subject during the study may be given at the discretion of the investigator. However, it is the responsibility of the investigator to ensure that details regarding the medication are recorded in full in the eCRF.

Subjects are allowed to continue taking csDMARDs therapy with stable doses (eg, no escalations or additions, initiated ≥ 4 weeks prior to the first dose of study drug) and no change in route of administration for the previous 4 weeks prior to Day 1 dosing. Furthermore, dose(s) must have been stable during any screening, or treatment periods, unless dictated by tolerability requirements, as indicated in inclusion criteria 4 (Section 4.1.1).

Subjects may choose to washout csDMARDs 30 days prior to Day 1 dosing except for leflunomide. Subjects who discontinued leflunomide and have had successful chelation with 8 g of cholestyramine (3 times daily) for 3 days must wait 4 weeks prior to the first administration of the study drug (Day 1). Subjects who discontinued leflunomide and did not have cholestyramine washout must wait 12 weeks after last dose of leflunomide prior to Day 1 dosing (Section 4.1.1).

Subjects are permitted to receive either oral or parenteral glucocorticoids (≤ 10 mg daily of prednisone/prednisolone or equivalent) and nonsteroidal anti-inflammatory drug, if they have received a stable dose for at least 28 days prior to Day 1 dosing and must not be changed (eg, no escalations or additions) during any washout, screening, or treatment periods, unless dictated by tolerability requirements. In addition, subjects are permitted to receive low-potency topical, otic, and ophthalmic glucocorticoid preparations provided the preparations are administered per the instructions on the product label.

Subjects taking MTX must also be receiving a folic acid (or equivalent, such as folinic acid) supplementation at a stable dose for at least 4 weeks prior to Day 1 dosing. Subjects should continue with their stable doses of folic acid throughout the study.

5.8.2 Prohibited Concomitant Medications

The medical monitor must be notified in advance (or as soon as possible thereafter) of any instances in which prohibited medications are administered.

Prohibited medications during the study include:

- Any biological agents other than TNF α inhibitor(s)
- Any csDMARDs other than those listed in the inclusion criteria
- Alkylating agents within 6 months prior to Day 1 dosing
- Prior treatment with intra-articular, intramuscular, intravenous, trigger point or tender point, intra-bursa, or intra-tendon sheath corticosteroids in the proceeding 8 weeks prior to Day 1 dosing

- Live or live-attenuated vaccine within 4 weeks prior to Day 1 dosing or expected need for live vaccination during study participation including at least 4 weeks after the last dose of study drug
- Combinations between MTX and leflunomide
- Known CYP1A2 and UGT1A1 inhibitors and inducers (see Appendix 13.1 for a list of suggested named CYP1A2 and UGT1A1 inhibitors and inducers) at least 4 weeks or 5 half-lives, whichever is longer, prior to Day 1 dosing
- High potency opiates including (but not limited to): oxycodone, oxymorphone, fentanyl, levorphanol, buprenorphine, methadone, hydromorphone, morphine, and meperidine at least 4 weeks prior to Day 1 dosing

6 Study Assessments and Procedures

Before performing any study procedures, all potential subjects will sign an ICF. Subjects will have the opportunity to have any questions answered before signing the ICF. The investigator must address all questions raised by the subject. The investigator will also sign the ICF.

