1.4 Placebo Rationale

The proposed study is a placebo-controlled, double-blind study of oral SKI-O-703 coadministered with background therapies for RA. The double-blind, placebo-controlled, randomized clinical study design is considered the gold standard for the safety and efficacy assessment of a new therapy both by clinicians and regulatory authorities. In this study subjects will be allowed to receive background medications for RA, including MTX, and other oral DMARDs, therefore subjects are also allowed to receive permitted concomitant medications in line with current standard of care (SOC) practices for RA. Any subject who cannot adhere to the protocol or who discontinues treatment will have an end-of-treatment (EOT) and will be followed for the intended duration of the study.

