4.1.1 Inclusion Criteria

Each subject must meet all the following criteria to be enrolled in this study:

1. Subject is an adult male or female aged ≥ 18 years old at time of signing the informed consent (or per local customs for ≥ 19 years of age for Korean subjects).
2. Subject has Body Mass Index (BMI) of ≥ 18 and $< 40 \text{ kg/m}^2$ at screening.
3. Subject who has a diagnosis of RA according to the 1987 ACR criteria (Appendix 13.2) or the 2010 ACR/EULAR classification criteria (Appendix 13.3) for at least 6 months prior to Day 1.
4. Subject has active disease at screening and baseline following treatment of RA with inadequate response to csDMARDs or anti-TNF α biological agent(s) as per 2012 update of the 2008 ACR RA treatment recommendations (Singh JA 2012).
 - a. Active disease is defined as:
 - presence of ≥ 5 swollen joints (of 28 assessed) and presence of ≥ 5 tender joints (of 28 assessed), and
 - serum hsCRP concentration $\geq 0.6 \text{ mg/dL}$ (or $\geq 6.0 \text{ mg/L}$; $1 \text{ mg/L} = 9.524 \text{ nmol/L}$) at screening (based on the upper limit of normal [ULN] of laboratory normal

range). Repeat may be allowed once during screening period (after an approval from medical monitor), if the result is considered unexplained/unexpected (eg, not corresponding with clinical disease activity or discordant with recent local result).

b. At least ONE of the following treatments for RA must have been received:

- anti-TNF α biological agent(s): Includes at least 1 of the following treatments, with completed washout period indicated prior to Day 1 dosing

adalimumab (Humira $^{\circledR}$)	60 days washout
etanercept (Enbrel $^{\circledR}$)	30 days washout
infliximab (Remicade $^{\circledR}$)	60 days washout
certolizumab pegol (Cinzia $^{\circledR}$)	60 days washout
golimumab (Simponi $^{\circledR}$)	60 days washout

- csDMARD therapy: Includes at least 1 of the following dosing regimen for at least 90 days of continuous use (prior to Day 1 dosing)*

- MTX 15 to 25 mg/week. If the current MTX dose is <15 mg/week, the subject's intolerance to \geq 7.5 mg dose must be documented in the subject's medical history
 - \leq 3000 mg/day (3 g/day) sulfasalazine
 - \leq 400 mg/day hydroxychloroquine
 - \leq 200 mg/day minocycline
 - \leq 20 mg/day leflunomide

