*Note: Combinations of up to 2 csDMARDs are allowed. However, combination of MTX and leflunomide is not allowed. Subjects are allowed to continue taking csDMARD therapy at stable doses (initiated \geq 4 weeks prior to the first dose of study drug) throughout the study period.

a) If subjects have to discontinue csDMARD therapy (except for leflunomide), the washout windows 30 days prior to Day 1 dosing must be observed.

b) If subjects have to discontinue leflunomide due to combination use with MTX before enrollment, the following washout windows must be observed: subjects who discontinued leflunomide and have had successful chelation with 8 g of cholestyramine (3 times daily) for 3 days must wait for 4 weeks prior Day 1 dosing. Subjects who discontinued leflunomide and did not have cholestyramine washout must wait 12 weeks after last dose of leflunomide prior to Day 1 dosing.

5. Subjects taking MTX while on study must be willing to take dietary supplement of oral folic acid (or equivalent, such as folinic acid) at a stable dose.
6. Subject who has adequate renal and hepatic function at screening as defined by the following clinical chemistry results:
 - a. Serum creatinine $<1.5 \times \text{ULN}$ or an estimated creatinine clearance level $\leq 50 \text{ mL/min}$ (by MDRD GFR equation)
 - b. Serum alanine aminotransferase (ALT) $<2.5 \times \text{ULN}$
 - c. Serum aspartate aminotransferase (AST) $<2.5 \times \text{ULN}$
 - d. Serum total bilirubin $<2 \times \text{ULN}$.

Repeat of clinical chemistry laboratory tests may be allowed once during screening period (after an approval from medical monitor), if the initial result is unexpected/unexplained (not due to a known underlying condition or concomitant medications or other known cause).

7. Subject who has the following hematology laboratory test results at screening:
 - a. Hemoglobin $\geq 8.5 \text{ g/dL}$ (International System of Units [SI]: $\geq 85 \text{ g/L}$ or 5.28 mmol/L)
 - b. White blood cell count $\geq 3.5 \times 10^3 \text{ cells}/\mu\text{L}$ (SI units: $\geq 3.5 \times 10^9 \text{ cells/L}$)
 - c. Neutrophil count $\geq 1.5 \times 10^3 \text{ cells}/\mu\text{L}$ (SI units: $\geq 1.5 \times 10^9 \text{ cells/L}$)
 - d. Platelet count $\geq 100 \times 10^3 \text{ cells}/\mu\text{L}$ (SI units: $\geq 100 \times 10^9 \text{ cells/L}$).

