4.1.2 Exclusion Criteria

Subject meeting any of the following criteria will be excluded from the study:

1. Subject is receiving or has previously received any treatment for RA other than the medications listed in the inclusion criteria for the treatment of RA. This includes but not limited to:
 - a. Prior exposure to any biological agent other than TNF α inhibitor(s).
 - b. Any prior use of SYK or Janus kinase (JAK) inhibitors.
 - c. Alkylating agents used within 6 months prior to Day 1 dosing.
 - d. Prior treatment with intra-articular, intramuscular, intravenous, trigger point or tender point, intra-bursa, or intra-tendon sheath corticosteroids in the proceeding 8 weeks prior to Day 1 dosing.
 - e. Any surgical procedure, including bone or joint surgery or synovectomy (including joint fusion or replacement) within 12 weeks prior to Day 1 dosing.
2. Live or live-attenuated vaccine within 4 weeks prior to Day 1 dosing or expected need for live vaccination during study participation including at least 4 weeks after the last dose of study drug.
3. Subject has had treatment with any other investigational device or medical product within 4 weeks or 5 half-lives prior to Day 1 dosing, whichever is longer.
4. Subject who (based on the investigator's clinical assessment, makes the subject an unsuitable candidate for the study) has any active or recurrent or history of any of the following infections:

- a. Hepatitis B virus (HBV): Serologic evidence of current/previous HBV infection based on the results of testing for hepatitis B surface antigen (HBsAg) and anti-hepatitis B core (anti-HBc) antibody as follows within 6 weeks of Day 1:
 - Subjects positive for HBsAg and/or positive for anti-HBc antibody (regardless of anti-HBs antibody status) are excluded.
- b. Hepatitis C virus (HCV): Positive test for antibody confirmed on a subsequent blood sample by RNA-PCR assay within 6 weeks of Day 1.
 - Subjects who are positive for hepatitis C antibody and negative for hepatitis C RNA-PCR assay performed on a subsequent sample will be eligible to participate.
 - Subjects who are positive for hepatitis C antibody and have a positive result for hepatitis C RNA-PCR assay performed on the subsequent sample will not be eligible to participate.
- c. Human immunodeficiency virus (HIV) 1 or 2: Positive test at screening.
- d. Mycobacterium tuberculosis (TB):
 - For subjects with a history of TB, they may be enrolled if the following conditions met:

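### Protocol 5.8.2 exempts TNF inhibitors from the biologics prohibited during the study, so with 5.8.1 an investigator may add anti-TNF during the 12-week treatment period

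*Protocol*

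**What the plan says.** Protocol 5.8.2 heads its list as applying during the study. The first bullet covers "Any biological agents other than TNF" α inhibitors. Protocol 5.8.1 sets the default for everything else: "Any concomitant medication, except the prohibited medications (Section 5.8.2), deemed necessary for the welfare of the subject during the study may be given", at the investigator's discretion. The same 5.8.2 asks that the medical monitor be told "of any instances in which prohibited medications are administered".

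Other sections bear on what was meant:

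- Exclusion criterion 1a (Protocol 4.1.2) uses nearly the same words for history: "Prior exposure to any biological agent other than TNF" α inhibitors.
- Inclusion criterion 4b (Protocol 4.1.1) accepts previous anti-TNF treatment "with completed washout period indicated prior to Day 1 dosing": 30 days for etanercept and 60 days for the other four listed agents.
- The note to 4b says "Subjects are allowed to continue taking csDMARD therapy at stable doses" throughout the study. It says nothing similar for anti-TNF.
- Protocol 1.4 describes background RA therapy as "including MTX, and other oral DMARDs". The same sentence then allows permitted concomitant medication consistent with standard care for RA.
- Protocol 5.8 requires that any medication a subject "receives during the study must be recorded" in the eCRF.

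On the analysis side, SAP 8.2.1 runs the primary ANCOVA on observed Week 12 values in the ITT set. SAP 5.2 and 7.1 leave the major deviations and the prohibited-medication list to be settled before database lock.

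**The concern.** An exception for TNF inhibitors makes sense when it decides who may enter: the trial deliberately admits patients whose anti-TNF treatment failed. In a list of drugs barred on study, the same words exempt a class that Protocol Section 1 itself describes as effective in RA. A site that reads 5.8.1 and 5.8.2 literally could add anti-TNF to blinded study drug and be within the protocol.

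The Week 12 score would then reflect study drug or placebo plus anti-TNF, and nothing in the primary analysis separates the two. Because the drug is not prohibited, its use would not trigger the notice to the medical monitor. It would not clearly be a deviation either, so removal from the per-protocol repeat is not assured.

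**Working it through.** The plan gives no figure on this point. The check is mainly textual, with one line of arithmetic for scale.

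**1. Is anti-TNF barred after Day 1 anywhere in the text reviewed?**

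- Inclusion 4b governs only the washout before Day 1.
- Exclusion 1a governs prior exposure.
- Exclusion 8 covers planned live vaccines, surgery and high-potency opiates.
- The rules against escalation or addition in 5.8.1 are written for csDMARDs, glucocorticoids and NSAIDs, not for biologics.
- 5.8.2 names TNF inhibitors only to except them.

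So no section reviewed bars it. The protocol appendices were not in the text available.

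**2. Does the open-ended wording of the 5.8.2 list help?** The list is introduced as including certain drugs, so it need not be complete. That could bring in a drug the list does not mention. It cannot readily bring in one the list expressly excepts. The next bullet has the same form: it bars csDMARDs other than those in the inclusion criteria, and there the excepted drugs really are allowed on study. A site would read the anti-TNF exception in the same way.

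**3. Does such a subject reach the primary analysis?** Under SAP 4.2, the Visit 5 EOT assessment counts as Week 12 only if the subject completed the treatment period. A subject who adds anti-TNF and completes treatment qualifies. If all three components were assessed, the value enters the ANCOVA of SAP 8.2.1. The sensitivity analyses in SAP 8.2.2 to 8.2.4 fill in missing values, or local hsCRP results set to missing. None addresses an observed value taken after added anti-TNF.

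**4. Scale.** Input: 37 completers per arm (Protocol 7.4, SAP 4.3). Let *k* be the number of completers in an arm who added anti-TNF and *g* the mean DAS28 change this causes in them. Approximately, under ANCOVA:

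- Shift in that arm's mean = *k* × *g* / 37. For *k* = 1 and *g* = 1: 1/37 = 0.027.
- Bias in the active-versus-placebo difference = (*k*₁*g*₁ − *k*₀*g*₀) / 37, with subscript 1 for active and 0 for placebo. Equal use with equal effect gives 0.
- To move the difference by 10% of the design value (0.10 × 0.80 = 0.08) takes 0.08 × 37 = 2.96, or about 3 net subject-points.

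More use on placebo would shrink the apparent benefit; more use on active would inflate it. The documents give neither *k* nor *g*, so no estimate of bias or power loss follows.

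**The case against.** The strongest reply is that this is only awkward wording. Much of 5.8.2 repeats entry criteria: alkylating agents, injected corticosteroids, CYP1A2/UGT1A1 drugs and opiates are all tied to periods before Day 1. Read strictly, JAK inhibitors are not named there either. Section 1.4 also refers to standard care for RA, so the intent to keep anti-TNF out is not beyond doubt. Use would be recorded, a physician or designee reviews deviations before lock, and the sponsor's designee finalizes the prohibited list. Harm requires a subject both to add anti-TNF and to complete 12 weeks of treatment.

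Most of this stands as a limit. The standard-of-care clause makes the intent a strong inference, not a certainty. The carry-over from entry criteria explains the error but does not remove it: JAK inhibitors are merely unmentioned, whereas TNF inhibitors are expressly excepted. Review before lock can classify use but cannot prevent it.

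A reader might infer more than the documents support:

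- *Subjects may enter while on anti-TNF.* They may not; the 4b washout protects baseline.
- *5.8.2 itself grants permission.* It does not. The permission comes from 5.8.1 and depends on the subject's welfare.
- *Use would be hidden.* Protocol 5.8 requires it in the eCRF.
- *The trial is biased or underpowered.* No rate or effect is given, and bias needs a difference between arms.
- *Anti-TNF should be barred through the end-of-study visit.* That would deny a standard treatment to subjects who have stopped study drug but remain in the study (Protocol 4.2.2). It would also cover four weeks after the last scheduled efficacy endpoint (Protocol 7.2).

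**Conclusion.** Wrong as written, and it should be corrected. The exception in 5.8.2, combined with the default in 5.8.1, allows anti-TNF to be added during the treatment period. That conflicts with the washout in inclusion 4b and with a continuation note that covers csDMARDs alone. If the rule is used, a Week 12 score taken on an active RA biologic enters the primary comparison, with no medical-monitor notice and no assured per-protocol exclusion.

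The size is unknown. What can be said is about 0.027 in an arm's mean per subject per DAS28 point, with bias only where use or its effect differs between arms. The conclusion rests on the text of the sections reviewed and on a strong but not certain reading of intent. It does not rest on any assumed rate of use.

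**What to change.** Reword the 5.8.2 bullet to: *Any biological agents, including TNF α inhibitors, from Day 1 while on study drug and until the Week 12 assessment (TNF α inhibitors also during the washout required by inclusion 4b); biological agents other than TNF α inhibitors remain prohibited through EOS.* Place no anti-TNF bar on subjects who have permanently stopped study drug or passed Week 12; their use is still recorded in the eCRF.

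SAP 7.1 contains no list to edit, so state there that the list to be finalized before lock will include on-treatment TNF inhibitors. State in SAP 5.2 that such use before Week 12 is a major deviation that excludes the subject from the per-protocol set, and that the subject stays in the ITT set. A repeat that sets values after the first on-treatment anti-TNF dose to missing, using the multiple imputation of SAP 8.2.3, is optional.

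The cost is one protocol bullet, carried through the usual amendment process, and two statements in the SAP. No new analysis is required, and the SAP statements can be made at any time before lock. There is one small downside: a subject who needs anti-TNF before Week 12 must stop study drug and then, under SAP 4.2, has no Week 12 value in the observed-case analysis.
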